2.2 SECONDARY OBJECTIVES

To compare the diagnostic impact of ⁶⁸Ga-PSMA-11 PET/CT imaging over current standard of care imaging modalities.

To compare the impact of ⁶⁸Ga-PSMA-11 PET/CT imaging over standard of care imaging on the therapeutic decision (minor and major therapeutic changes) with regards to the number and/or lesion location.

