3.1.2 Secondary Objective

Determine the frequency of positive PSMA PET scans in relation to the PSA value before the PSMA scans and compared to conventional imaging. Results will be summarized descriptively with 95% confidence intervals.

Determine rate of major and minor changes in management by comparing planned management strategy using conventional imaging and executed management strategy incorporating information from ⁶⁸Ga-PSMA-11 PET/CT, regardless of treatment modality.

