4.4 IMAGE ANALYSIS AND INTERPRETATION

A board-certified nuclear medicine physician or nuclear radiologist on-site will interpret the images of the ⁶⁸Ga-PSMA-11 PET/CT scan. Images will be corrected for attenuation and scatter and adjusted for system sensitivity and will provide parametric images in terms of standardized uptake values (SUV) (= MBq found/gm tissue / MBq injected/gm body mass).

PET imaging can be combined with a low-dose CT for attenuation correction, a diagnostic CT (PET/CT), or MRI (PET/MR). Patients may undergo a diagnostic MRI of the prostate, other body parts or a whole-body MRI at the same imaging session as clinically indicated. Contrast material may be administered for the CT or MRI as clinically indicated.

Imaging will be initiated at approximately 60 minutes (45-120 minutes) following administration of the PSMA radiopharmaceutical. At the discretion of the investigator, an additional image of the pelvis may be obtained.

Patients will receive a single dose of ⁶⁸Ga-PSMA-11 and undergo a PET/CT or PET/MRI imaging study. At the time of interpretation of the ⁶⁸Ga-PSMA-11 PET study, the reviewing nuclear medicine physician and/or radiologist will compare the ⁶⁸Ga-PSMA-11 PET findings with the results from previously performed standard-of-care imaging for prostate cancer staging. The presence or absence of sites suspicious for recurrent prostate cancer will be documented. (e.g., prostate bed, lymph nodes, metastases to bone or other organs).

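### The only PET read described is made alongside prior standard imaging, so the comparison of PET with conventional positivity is open to reader bias of uncertain direction

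*Combined protocol and SAP*

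**What the plan says.** Section 2.2 sets a comparative secondary objective: "To compare the diagnostic impact of" PSMA PET/CT "imaging over current standard of care imaging modalities". Section 3.1.2 turns it into an endpoint: "Determine the frequency of positive PSMA PET scans in relation to the PSA value before the PSMA scans and compared to conventional imaging". The analysis is descriptive: "Results will be summarized descriptively with 95% confidence intervals".

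Section 4.4 describes how the PET result arises. "A board-certified nuclear medicine physician or nuclear radiologist on-site will interpret the images". At the time of interpretation, the reviewing physician compares the PET "findings with the results from previously performed standard-of-care imaging for prostate cancer staging". The next sentence reads: "The presence or absence of sites suspicious for recurrent prostate cancer will be documented".

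Nowhere do the documents describe a PET call made before that comparison, a read blinded to prior imaging, an independent or central read, a re-read of the conventional images, a criterion for a positive scan, or a reference standard for positive sites. Section 4.5.2 gives an analysis for change in management only.

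**The concern.** The two results being compared are produced with unequal information. The conventional scans were done earlier, so their reports were made without the PET. The PET reader has those reports to hand. A PET result recorded this way is PET interpreted with conventional imaging, set against conventional imaging alone.

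The prior result can act on the PET call in two ways:

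- **Upgrading.** A lesion already known from CT, MRI or bone scan can turn an equivocal PET focus into a positive call. This shrinks the cell of men positive on conventional imaging and negative on PET.
- **Downgrading.** A clean prior scan can lead the reader to dismiss an equivocal focus seen only on PET. This shrinks the cell of men positive on PET and negative on conventional imaging.

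Those two cells are what the 3.1.2 comparison is meant to show. If both are pulled toward agreement, the study could overstate or understate what PET adds, and the recorded data could not show which. The planned confidence intervals cover sampling error only.

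**Working it through.** The plan gives no expected positivity rate, test or power calculation for this comparison, and section 4.5.3 declines a sample size calculation. There is no figure to reproduce. The check below asks only whether the design fixes the direction of the bias, and on what scale it might lie.

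**Inputs, per 100 men**

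- Number of men: 100, the planned enrolment (synopsis, 4.5.3).
- Conventional positivity: 10, the upper end of the yield below 10% given in section 1. That figure concerns early relapse at low PSA and does not describe the staging or metastatic groups, so using it for all men is an assumption.
- PET positivity without knowledge of priors: 30, 50 or 70 (assumed).
- Share *s* of conventional-positive men who are also PET-positive without that knowledge: 0.6 or 0.9 (assumed).
- *u*: share of conventional-only men upgraded to PET-positive (assumed).
- *d*: share of PET-only men downgraded to PET-negative (assumed).

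**Cells**

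Both positive = 10 × *s*. Conventional-only = 10 − both. PET-only = PET positives − both.

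| *s* | Both | Conventional-only | PET-only at 30 / 50 / 70 |
|---|---|---|---|
| 0.6 | 6 | 4 | 24 / 44 / 64 |
| 0.9 | 9 | 1 | 21 / 41 / 61 |

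**Shift in PET positivity**

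Shift = *u* × conventional-only − *d* × PET-only. The PET-minus-conventional difference moves by the same amount, because the conventional rate is unchanged.

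| Behaviour | Arithmetic at the extremes | Shift, points |
|---|---|---|
| Upgrade only, *u* = 1 | 1 × 1; 1 × 4 | +1 to +4 |
| Downgrade only, *d* = 0.10 | −0.10 × 21; −0.10 × 64 | −2.1 to −6.4 |
| Downgrade only, *d* = 0.20 | −0.20 × 21; −0.20 × 64 | −4.2 to −12.8 |
| Both, *u* = 1, *d* = 0.05 | 1 − 0.05 × 61; 4 − 0.05 × 24 | −2.05 to +2.8 |

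The sign depends on the assumed behaviour of the reader, not on the design.

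**A small net shift can hide a larger loss of discordance.** Take PET positivity 50, *s* = 0.6, *u* = 1, *d* = 0.10. Conventional-only goes from 4 to 0 and PET-only from 44 to 39.6. The difference moves from 40 to 39.6 points (−0.4), while the discordant total falls from 48 to 39.6 men (−8.4).

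**Upgrading only, with more conventional positives.** Assume 30 men positive on conventional imaging, 10% to 20% of them missed by PET alone (3 to 6 men), and 30% to 60% of those misses upgraded. PET positivity rises by 3 × 0.3 = 0.9 to 6 × 0.6 = 3.6 points. The conventional-only cell ends between 3 × 0.4 = 1.2 and 6 × 0.7 = 4.2 men. With 10 conventional positives, the same rates give 1 × 0.3 = 0.3 to 2 × 0.6 = 1.2 points.

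**Scale.** The exact 95% interval at n = 100 is 39.8% to 60.2% for 50 positives and 4.9% to 17.6% for 10. Most of the shifts are smaller than the half-width at 50 positives, about 10 points.

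**The case against.** There is a fair case for leaving the plan alone. The protocol exists to give clinical access, and its primary endpoint is safety. The affected endpoint is secondary and descriptive, with no test or decision rule, and most of the plausible shifts lie within sampling error at 100 men. Reading with priors is also the intended practice: added value over standard imaging is naturally PET plus priors against priors alone. All of this stands as an argument for low severity and a light remedy. It does not settle the 3.1.2 endpoint, which sets the positivity of PET scans against that of conventional imaging and does not say that the PET result already includes the priors.

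It can also be said that section 4.4 fixes no order between forming the PET call, comparing and documenting. That is correct. A reader might infer that the plan has the result recorded only during the comparison. The text does not say so. What can be said is that the plan specifies no call made before it.

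A reader might also infer that the comparison is biased toward PSMA PET. The documents do not support that. Upgrading favours PET, downgrading works against it, and a calculation that models upgrading alone has its direction built in. Even such a calculation leaves 1.2 to 4.2 men in the conventional-only cell under the 30-positive assumptions, so it would be wrong to say that the cell is emptied. With no reference standard, neither sign nor size can be recovered.

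**Conclusion.** The point holds in a limited form. The one PET read described is made with prior standard imaging results to hand, no earlier PET call is specified, and the result enters a stated comparison with that same imaging. The 3.1.2 positivity comparison is therefore open to reader bias of uncertain direction and size. Under the assumptions shown, the net shift runs from −12.8 to +4 points. All reader-behaviour rates are assumed, and the 10% conventional yield is borrowed from a low-PSA setting.

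It would be an over-reading to extend this to change in management (3.1.2, 4.5.2). That endpoint compares the plan based on conventional imaging with the management carried out once PET information is added. Reading PET with the priors is part of the strategy it measures, so it is unaffected.

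Severity is minor, and the remedy is a cheap improvement.

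**What to change.** In section 4.4, add a sentence requiring the same reader to enter and lock the overall PET result and the positive sites (prostate bed, nodes, bone, other) on the study form before opening prior imaging. The reader then makes the comparison and issues the clinical report as now.

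In section 3.1.2, state that the positivity comparison uses the locked entry, and describe any result taken from the later read as PET read with knowledge of prior imaging. With both entries on file, the calls changed in each direction can be counted.

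Cost: one short form entry and a few minutes of reader time per scan. No second reader is needed and the clinical read does not change.

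Protection is partial. Section 4.4 allows a diagnostic CT or MRI in the same session, so the locked entry may still draw on conventional anatomical imaging. In some men, such as those scanned to assess response of metastatic disease (synopsis), the indication itself reveals prior disease. Both situations should be noted on the form so that they can be identified when results are reported.

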4.5 STATISTICAL CONSIDERATIONS

4.5.1 Primary Objective

Determine the safety and tolerability of ⁶⁸Ga-PSMA-11 using the following primary safety outcome measures: Incidence and nature of AEs and change in clinical laboratory results. Incidence and severity of AEs and adverse events will be estimated with 95% confidence intervals summarized with descriptive statistics.

4.5.2 Secondary Objective

Determine rate of overall changes in management by comparing planned management strategy using conventional imaging with executed management strategy incorporating information from ⁶⁸Ga-PSMA-11 PET/CT, regardless of treatment modality.

Analysis: The rate of change in management based on the incorporation of ⁶⁸Ga-PSMA-11 PET/CT results will be expressed as the percentage of total patients imaged in which change in management occurred, regardless of treatment modality. The rate of change in management will also be estimated within each group (initial staging, biochemical recurrence, and pre/post treatment). 95% confidence intervals (CIs) will be used to express precision of the estimates.

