4.2 PATIENT ASSESSMENTS

4.2.1 Symptom assessment pre- and post-imaging

A directed review of symptoms (nausea, fatigue, pain) will be graded against CTCAE to provide baseline evaluation prior to injection and assess for adverse events post-injection.

4.2.2 Change in management surveys.

Referring clinicians will be queried in providing information on how PSMA PET/CT results impacted the clinical management of patients.

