10. APPENDICES

APPENDIX A: STUDY CALENDAR: SCHEDULE OF ACTIVITIES

	Screening	Day of Scan	Post Scan
Informed Consent	X		
Standard of Care Chart Review	X		
Administration of Ga-PSMA PET Imaging		X	
Safety Monitoring		X	X
Change in management surveys		X	X

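### The change-in-management rate needs a plan based on conventional imaging, but nothing secures a definite one or says how a plan that waits for PSMA PET is scored, so the rate can be biased, plausibly upward

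*Combined protocol and SAP*

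**What the plan says.** The endpoint appears twice. Section 3.1.2 reads "Determine rate of major and minor changes in management by comparing planned management strategy using conventional imaging and executed management strategy", the latter informed by PSMA PET. Section 4.5.2 restates it for overall change, "comparing planned management strategy using conventional imaging with executed management strategy". Both name a plan resting on conventional imaging as the comparator.

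Section 4.5.2 then says that the rate "will be expressed as the percentage of total patients imaged in which change in management occurred, regardless of treatment modality". It asks for the same rate within three groups (initial staging, biochemical recurrence, pre/post treatment), with 95% confidence intervals.

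On data collection, section 4.2.2 has one sentence: "Referring clinicians will be queried in providing information on how PSMA PET/CT results impacted the clinical management of patients". In Appendix A the row "Change in management surveys" is marked at Day of Scan and Post Scan but not at Screening. Screening carries informed consent and "Standard of Care Chart Review"; what that review abstracts is not stated.

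Section 4.5.3 anticipates 100 patients and gives no sample size calculation.

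**The concern.** The comparison is meaningful only if its first term is what the clinician would have done on conventional imaging alone. In an access protocol, where the man has come in order to have a PSMA PET, a truthful answer to a question about the current plan may be to decide once the scan is read. That is not a plan on conventional imaging. Care carried out after the scan cannot match it, so a literal comparison of plan with executed care records a mismatch. This happens even when the treatment given is the one conventional imaging would have led to.

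The reported rate, overall and by group, could then partly measure how often clinicians deferred and not how often PSMA PET altered care. The confidence interval would not show this, because it reflects sampling error only. The comparator also cannot be reliably rebuilt once the PET result is known, so the gap has to be closed when the data are collected.

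**Working it through.** **What the text secures**

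| Needed for the endpoint | What the documents provide |
|---|---|
| A definite plan on conventional imaging | Named in 3.1.2 and 4.5.2; no instrument in 4.2.2 is described as recording it |
| The plan recorded before the PET result | Survey marked on the day of scan; order relative to the result not stated |
| A rule for what counts as a change | None; major and minor are named in 3.1.2 but not defined |
| Handling of undecided or PET-contingent plans | None |
| Denominator | All patients imaged (4.5.2) |

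**Size**

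The plan gives no expected rate, so there is no figure of its own to reproduce. What follows is an illustration.

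Inputs:
- N = 100 (section 4.5.3).
- u = share of men whose recorded plan is to wait for PSMA PET. Assumed, 10-30%.
- c = change rate among men with a definite plan. Assumed, 30-70%.

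Changes among men with a definite plan: x = c(1 - u)N.

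Three ways to score the deferrals:
- As change: (x + uN)/N = c + u(1 - c)
- As no change: x/N = c - uc
- Excluded: x/(N - uN) = c

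Results for c = 50%, with exact (Clopper-Pearson) 95% intervals:

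| u | As change | As no change | Excluded |
|---|---|---|---|
| 10% | 55/100 = 55% (44.7-65.0) | 45/100 = 45% (35.0-55.3) | 45/90 = 50% (39.3-60.7) |
| 20% | 60/100 = 60% (49.7-69.7) | 40/100 = 40% (30.3-50.3) | 40/80 = 50% (38.6-61.4) |
| 30% | 65/100 = 65% (54.8-74.3) | 35/100 = 35% (25.7-45.2) | 35/70 = 50% (37.8-62.2) |

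Relative to exclusion, over the whole assumed range:
- Scored as change, the shift is +u(1 - c): from 0.10 × 0.30 = +3 points to 0.30 × 0.70 = +21 points.
- Scored as no change, the shift is -uc: from 0.10 × 0.30 = -3 points to 0.30 × 0.70 = -21 points.

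The gap between the two scorings is always u. At u = 20% it is 20 points, about the full width of the interval for 50/100 (39.8-60.2%).

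**If deferring men differ from the rest**

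Exclusion recovers the overall rate only if the deferring men would have changed as often as the others. Suppose c = 40%, u = 20%, and 70% of the deferring men would truly have changed (all assumed).
- True overall rate: 0.80 × 40% + 0.20 × 70% = 46%
- Scored as change: 32% + 20% = 52%
- Scored as no change: 32%
- Excluded: 40%

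No single scoring gives 46%, but the range from 32% to 52% contains it. The all-change and no-change scorings always bracket the overall rate, because they set the unknown part to its two extremes.

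**The case against.** The strongest reply is that the documents never say a deferral counts as a change. No such response option is shown, the survey form is not included, and change is not defined. The endpoint names a plan on conventional imaging, so a deferral arguably does not satisfy it, and counting one would depart from the text. Section 4.5.2 also ties the change to use of the PET results. This stands in part: a reader might infer that deferrals count automatically and that the rate is inflated, and the documents establish neither. With all patients imaged in the denominator, scoring deferrals as no change would lower the rate. The link to PET results does not remove the upward risk, though, since a clinician who waited for the scan did use it.

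A reader might also blame the day-of-scan timing. That does not hold. Consent to this PSMA PET study is taken at Screening, so the scan is already expected then, and an earlier survey could still record a deferral. The chart review at Screening might capture an earlier plan, but nothing says that it does.

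A third tempting inference is that the problem is worst in early biochemical relapse, because section 1 gives a yield below 10% for standard imaging at low PSA. That figure is an imaging yield, not a share of deferred plans. The same section says salvage radiotherapy is routinely given on a rising PSA, so definite plans may be common in that group.

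Finally, the endpoint is secondary and descriptive, in a protocol run for access. That limits the weight of the point. It does not supply the missing comparator.

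**Conclusion.** The point holds as a cheap improvement. The endpoint depends on a plan made on conventional imaging, and the protocol neither requires a definite one nor says how an undecided or PET-contingent plan is scored. Under a literal plan-versus-executed comparison such plans can count as changes, so the rate can be biased, plausibly upward. Neither the direction nor the amount is fixed by the text.

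The shifts of 3 to 21 points in either direction rest on assumed deferral shares of 10-30% and assumed change rates of 30-70%. They are measured against exclusion, which equals the overall rate only if deferring men are like the others. They show how much the unwritten rule could matter, not how much it will. No hypothesis test or sample size is affected.

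**What to change.** **Sections 4.2.2 and Appendix A.** Before the PSMA PET result is known, have the referring clinician record the management they would carry out on conventional imaging if PSMA PET were not available. Awaiting PSMA PET is not accepted as the plan. Appendix A should show where this item is collected.

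**Section 4.5.2.** Base the main rate on men with a definite plan, stating numerator and denominator. Report men who still have no definite plan in a separate row. Add a sensitivity range over all patients imaged, with the undecided men scored first as all change and then as no change.

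**Cost.** One survey question, one calendar entry and a short addition to the analysis text. The stated plan will be hypothetical for some men, the main denominator may be slightly smaller, and the reported rate may be lower.

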4.5.3 Sample Size and Power Estimate

Since this protocol is for clinical access only, there is no need for sample size and power estimation calculations. It is anticipated that 100 patients will be imaged with primary diagnosis of prostate cancer or biochemically recurrent prostate cancer. There will likely be a ramp up period in the number of patients who will be scanned.

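### Change in management is defined as planned versus executed strategy, but nothing requires the plan to be recorded before the PET result is released, or says how imaged patients without management data are counted

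*Combined protocol and SAP*

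**What the plan says.** The endpoint is a comparison of two strategies. Section 3.1.2 reads "Determine rate of major and minor changes in management by comparing planned management strategy using conventional imaging and executed management strategy", the latter incorporating PET information. Section 4.5.2 repeats this as "comparing planned management strategy using conventional imaging with executed management strategy incorporating information from" the PET/CT.

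For the analysis, 4.5.2 says that the rate will be "expressed as the percentage of total patients imaged in which change in management occurred", overall and within three groups (initial staging, biochemical recurrence, pre/post treatment), and that "95% confidence intervals (CIs) will be used to express precision of the estimates". It names no data source.

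The instrument is described once, in 4.2.2: "Referring clinicians will be queried in providing information on how PSMA PET/CT results impacted the clinical management of patients". Appendix A lists "Standard of Care Chart Review" at Screening and "Change in management surveys" at Day of Scan and Post Scan. Section 4.5.3 gives the expected size: "It is anticipated that 100 patients will be imaged with primary diagnosis of prostate cancer or biochemically recurrent prostate cancer".

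**The concern.** A planned-versus-executed comparison needs two records per patient, and the first must be made without knowledge of the PET result. The question in 4.2.2 asks for something else: the clinician's own account of what the result did to management. If that account is the only record, the plan has to be recalled or inferred once the result is known. A clinician may then overstate the effect of the scan, or may come to regard the executed strategy as what was intended all along.

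The second gap is in the counting. The denominator in 4.5.2 is everyone imaged. A patient with no planned or no executed strategy on record is in that denominator and cannot be shown to have changed. The protocol does not say whether such a patient is counted as unchanged, left out or reported separately.

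What is at stake is the meaning of the estimate, not power or type I error. The planned 95% CI reflects sampling variation only and covers neither problem.

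**Working it through.** **No figure to reproduce.** Section 4.5.3 gives no sample-size, power or precision calculation. The only numerical inputs from the documents are 100 patients imaged (4.5.3) and the 95% level (4.5.2). Every change rate, completeness rate and error rate below is an assumption for illustration.

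**Step 1: definition against data collection.**

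| Needed by 3.1.2 and 4.5.2 | What the documents provide |
|---|---|
| Plan based on conventional imaging, unaffected by PET | Chart review at Screening, with no statement that the plan is extracted; a Day of Scan survey whose content and timing relative to the result are not stated |
| Executed strategy after PET | A Post Scan survey with no stated time |
| Comparison of the two | A question on how PET results affected management (4.2.2) |
| Rule for imaged patients lacking either record | None |

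Section 4.4 has the image reader compare PET with earlier imaging, but that concerns lesions, not management.

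**Step 2: plan reconstructed after the result.** Let p be the true rate, fp the share of truly unchanged patients reported as changed, and fn the share of truly changed patients reported as unchanged. The reported rate is p(1 − fn) + (1 − p)fp. With p = 0.50:
- fp = 0.10 to 0.20, fn = 0: 0.55 to 0.60
- fn = 0.10 to 0.20, fp = 0: 0.45 to 0.40
- fp = fn: 0.50

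Neither direction nor size can be fixed from the documents.

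**Step 3: patients without management data.** Let N be imaged, m without data, and x changed among those with data. The possible rates are x/(N − m) among those with data, x/N with missing as no change, and (x + m)/N with missing as change. The last two differ by m/N, whatever x is. With N = 100 and 50% changed among those with data:

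| m | x | Among those with data | Missing = no change | Missing = change |
|---|---|---|---|---|
| 10 | 45 | 45/90 = 50% | 45% | 55% |
| 20 | 40 | 40/80 = 50% | 40% | 60% |
| 30 | 35 | 35/70 = 50% | 35% | 65% |

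For scale, the Wilson 95% CI for 50/100 is 40.4% to 59.6%, or 19.2 points wide. The spread between counting rules is about that wide at 20% missing and about half as wide at 10%. If chart review supplies every missing outcome, m = 0 and the spread vanishes.

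**Step 4: is the rate among patients with data enough?** Take 50 truly changed and 50 truly unchanged patients.
- Data on 90% of the changed and 70% of the unchanged: 45 + 35 = 80 with data. The rate among them is 45/80 = 56.3%, the all-imaged rate is 45%, and the bounds are 45% to 65%.
- Reversed: 35 + 45 = 80 with data. The rate among them is 35/80 = 43.8%, the all-imaged rate is 35%, and the bounds are 35% to 55%.

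In the first case the all-imaged rate is nearer the assumed 50% (5 points off against 6.3). In the second the rate among those with data is nearer (6.2 points off against 15). Neither is uniformly better, which is the reason to report both. That the bounds contain 50% is true by construction.

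**The case against.** The case for leaving the plan alone has substance. The comparator is by definition a plan made on conventional imaging, and 4.4 describes that imaging as already performed. Two survey points plus a Screening chart review fit a before/after design, and a Day of Scan survey is hard to explain if the only question is retrospective. The survey form is not in the documents, nor are the visit worksheets mentioned in 6.2.8, so a dated plan may well be captured. The study exists to provide access with safety monitoring, and this endpoint carries no test. The magnitudes rest almost wholly on assumed rates.

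Most of this stands, and it rules out two stronger readings that a reader might infer. The first is that the plan will in fact be reconstructed after the result. The documents do not show that; they show only that nothing prevents it. The second is that unreturned surveys count as no change, so that the rate is biased downward. Section 4.5.2 does not state that rule, does not name the survey as the only source, and does not exclude reporting on patients with data only.

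What does not stand is that the gap is mere missing detail. Someone who follows 4.2.2 as written collects an attribution made after the result, which is not the comparison that 4.5.2 defines. A Screening chart review, even if it holds the plan, cannot supply management executed after PET. The access purpose explains the absence of a power calculation, but the protocol still commits to this rate, three group rates and their CIs.

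**Conclusion.** The point holds in limited form. The protocol defines a before/after comparison but does not require the before record to predate the result, and it fixes a denominator without a rule for imaged patients who lack management data.

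Bias from a reconstructed plan could go either way, and its size is unknown. The effect of the missing counting rule equals the fraction without data: 20 points if 20 of 100 lack data (assumed), zero if charts fill every gap. The same holds within each of the three groups, where unequal completeness could create an apparent difference. With a 50% rate in both groups and 90% and 70% completeness (assumed), the all-imaged rates would read 45% and 35%.

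The endpoint is secondary and descriptive. No primary conclusion, test or sample size depends on it. It should still be settled before enrolment, because a plan not recorded before the result cannot later be recovered free of knowledge of it.

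**What to change.** **4.2.2 and Appendix A.** Make the Day of Scan survey a dated intended-management record, completed before the PET result is released. If it is not returned, take the plan only from chart entries dated before the result. Do not hold back the result for the form. If neither source gives a plan, count the patient as lacking a valid plan. Record executed management in the Post Scan survey at a stated time, with chart review as the fallback.

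**4.5.2.** Keep the all-imaged denominator. Overall and by group, report the number with both records, the rate among them with its 95% CI, and bounds over all patients imaged that count those without data first as no change and then as change.

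**Cost.** One short form in an existing survey slot, wording in three places, and some chart-review time. The CI for patients with both records is slightly wider: at an assumed 50% rate and 80% completeness, Wilson 39.3% to 60.7% (40/80) against 40.4% to 59.6% (50/100). That rate remains open to selective response, so it should not be shown without the bounds.
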